## **Objectives**

List your research objectives. Please include a summary of intended research objectives in the box below.

Primary Objective

To determine the Maximum Tolerated Dose of Epidiolex (CBD) in patients with biochemically recurrent prostate cancer

Secondary Objectives

To fully assess the safety and tolerability of CBD in patients with biochemically recurrent prostate cancer.

To measure change in serial PSA and testosterone levels from baseline throughout the treatment period as an indication of biochemical response

To assess health-related quality of life (EORTC QLQ C-30 and PR-25)

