The secondary endpoints include assessment of biochemical response via serial PSA and serial testosterone levels, and health-related quality of life (as assessed by the EORTC QLQ C-30 and PR-25).

The correlative endpoint includes CBD receptor 1 and 2 expression levels.

Sample Size/Accrual Rate

We plan to enroll up to 9 DLT evaluable patients for dose escalation to establish the MTD.

Once we have established the MTD, we will begin treating 6 to 9 more patients at the MTD level in an expansion cohort to confirm safety and explore evidence of efficacy of the study treatment. The number of patients to be enrolled in expansion cohort depends on the number of non-DLT evaluable patients in the dose escalation part of the study. If all patients in the dose escalation part of the study are DLT evaluable, we will have enroll 9 more patients, otherwise, we will subtract the number of non-DLT evaluable patients from expansion cohort. The total sample size for this study is 18 (enrolled) patients with about 12 patients treated at the MTD.

Analysis of Primary Endpoint

The dose escalation and MTD will be determined by the posterior distribution of Pr(DLT) estimate [41]. The target toxicity probability is set at 30%. Safety and tolerability of Epidiolex will be monitored and assessed. AE counts will be summarized by descriptive statistics.

Analysis of Secondary Endpoints

Change of PSA and testosterone levels from baseline throughout the 90-day treatment period will be represented by longitudinal

profiles and analyzed by mixed effects model. Baseline is defined as the last non-missing PSA measurement prior to administrating study drug. PSA and testosterone levels may be categorized and summarized by response rates with confidence intervals.

The Quality of Life scores collected longitudinally will be analyzed using appropriate linear models for repeated measures data.

Analysis of Correlative Endpoints

Post-hoc analyses will be conducted on correlative endpoints with appropriate statistical methods depending on distribution and availability of collected data.

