# 9. STATISTICAL CONSIDERATIONS

# 9.1 Study Design/Endpoints

This is a phase I dose escalation study with expansion cohort. Dose escalation will be determined by a Bayesian optimal interval (BOIN) design [41]. The target DLT rate is 30%. Patients are enrolled in cohorts with 3 patients in each cohort. Enrollment will be temporarily halted after the last patient of each cohort is enrolled until all current patients are DLT evaluable or withdrawn from the study. A patient will be considered DLT evaluable if he completes at least 75% of the planned dose of Epidiolex in the first 30 days of the treatment, unless the reason is due to toxicity.

The primary objective is to evaluate the acute toxicity and long-term safety and tolerability of Epidiolex (CBD) in patients with biochemically recurrent prostate cancer. Acute toxicity of Epidiolex is evaluated through DLT rate, which is calculated as the total number of patients experienced DLTs at a dose level divided by the total number of patients treated at the corresponding dose level. The calculation of DLT rate will only include DLT evaluable patients. Patients who are not DLT-evaluable will not be replaced for the current cohort and will not be included in the calculation of DLT rate. At the end of the dose escalation part of the study, we will use the dose escalation/de-escalation decision rules (see section 9.1.1) to decide the dose level for dose expansion cohort. If the current dose at the end of dose escalation is already the highest available dose, and the decision rules did not indicate de-escalation or elimination, the highest dose level is deemed as safe for acute toxicity; otherwise, the dose recommended by the decision rule is the estimated MTD.

Following dose-escalation, an expansion cohort will be enrolled to confirm safety for acute toxicity, evaluate long-term safety and tolerability and explore evidence of efficacy of the study treatment. Long-term safety and tolerability are evaluated through the summary statistics of adverse events occurred within the 90-day follow-up period in patients who received any amount of study drug. The study treatment is deemed as not safe for long-term tolerability if any of the following criteria are met:

- More than 40% of the patients treated at the dose level selected for expansion cohort experienced grade 3 or higher AEs that are possibly/probably/definitely related to study treatment

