#### 9.1.1 Dose Escalation / De-escalation Decision Rule

	Number of patients Treated									
Decision Rule	1	2	3	4	5	6	7	8	9	
Escalate (or highest) if # DLT <=	0	0	0	0	1	1	1	1	2	
De-escalate (or lowest) if # DLT >=	1	1	2	2	2	3	3	3	4	
Eliminate (or stop) if # DLT >=			3	3	4	4	5	5	5	

Note: the next cohort will be treated at the current dose level if the criteria are not met for escalation/de-escalation rules.

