# 9.2 Sample Size/Accrual Rate

We plan to enroll up to 9 DLT evaluable patients for dose escalation. If 3 or more of the first 9 patients are not evaluable for DLT, additional cohort(s) will be enrolled to ensure at least 9 DLT evaluable patients for dose escalation. Once we have established the highest tolerated dose is deemed as acceptable for acute toxicity or estimated the MTD, we will begin treating 6 to 9 more patients in an expansion cohort to confirm safety for acute toxicity, evaluate long-term tolerability and explore evidence of efficacy of the study treatment. The number of patients to be enrolled in expansion cohort depends on the DLT rate during the dose escalation part of the study. The total planned sample size for this study is 18 (enrolled) patients with about 12 patients treated at the MTD or the highest planned dose.

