# 9.3 Analysis of Primary Endpoint

Dose escalation decisions and MTD are estimated through the rules specified in section 9.1.1. DLT rate at each dose level will be calculated along with the Fisher's exact confidence interval at 95% confidence level. AE, SAE and AE of special interests will be summarized by descriptive statistics to evaluate long-term safety.

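### Sections 9.1 and 9.3 take the escalation table's last next-cohort output as the estimated MTD, and no supplied passage lets the expansion data revise it

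*Combined protocol and SAP*

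**What the plan says.** The Objectives section of the IRB application gives the primary objective as "To determine the Maximum Tolerated Dose of Epidiolex (CBD) in patients with biochemically recurrent prostate cancer". SAP section 9.1 words the primary objective as acute toxicity plus long-term safety and tolerability, but section 9.3, which covers the primary endpoint, still states: "Dose escalation decisions and MTD are estimated through the rules specified in section 9.1.1".

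Table 9.1.1 sets escalate, de-escalate and eliminate boundaries from the DLT count at the dose currently being given. Its note adds that "the next cohort will be treated at the current dose level if the criteria are not met for escalation/de-escalation rules". Section 9.1 uses the same table at the end of escalation "to decide the dose level for dose expansion cohort". If the current dose is the highest and the table does not call for de-escalation or elimination, that dose is declared safe for acute toxicity; "otherwise, the dose recommended by the decision rule is the estimated MTD".

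The Study Design section of the IRB application says something else: "The dose escalation and MTD will be determined by the posterior distribution of Pr(DLT) estimate [41". It gives no algorithm.

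The expansion of 6 to 9 patients follows, in the words of section 9.2, "Once we have established the highest tolerated dose is deemed as acceptable for acute toxicity or estimated the MTD". Its stated purposes include confirming acute safety. About 12 patients are expected at the MTD or highest planned dose.

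**The concern.** A next-cohort rule answers the question of where to put the next three patients, using the current dose alone. An MTD estimate answers which level best matches the 30% target, given everything observed. Sending a further cohort to a new level, or back to one with 2/3 DLTs, is an ordinary escalation step. Calling that level the estimated MTD is a different statement.

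The label is attached before the expansion. The expansion is meant to confirm acute safety, yet the supplied text has no step at which its DLTs could move the label or withdraw the declaration of acute safety for the top dose. At stake is the stated result for the objective named in the IRB application. Two analysts could also report different MTDs, one following the SAP and the other the posterior wording.

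**Working it through.** **Inputs.** Target DLT rate 30%, cohorts of 3 (section 9.1); up to 9 DLT-evaluable patients in escalation (section 9.2); boundaries from Table 9.1.1. At n = 3, 6, 9 these are: escalate at ≤0, ≤1, ≤2; de-escalate at ≥2, ≥3, ≥4; eliminate at ≥3, ≥4, ≥5.

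**Reproducing the table.** The usual BOIN settings (assumed) are φ = 0.30, φ1 = 0.6φ = 0.18, φ2 = 1.4φ = 0.42.
- λe = ln[(1−φ1)/(1−φ)] / ln[φ(1−φ1)/(φ1(1−φ))] = ln(0.82/0.70)/ln(0.246/0.126) = 0.2365
- λd = ln[(1−φ)/(1−φ2)] / ln[φ2(1−φ)/(φ(1−φ2))] = ln(0.70/0.58)/ln(0.294/0.174) = 0.3585
- Eliminate if Pr(p > 0.30 | data) > 0.95 under a Beta(1,1) prior, n ≥ 3.

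All three rows match for n = 1 to 9, so the table is sound. At 2/3 DLTs Pr(p > 0.30) = 0.916, below 0.95, so that level is not eliminated and can be named again.

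**Paths within 9 patients, starting at the lowest level.**
- *Level not yet given.* Level 1 at 2/9 meets the escalate boundary, so level 2 is named. With three levels, level 1 0/3 then level 2 1/6, or level 1 1/6 then level 2 0/3, names level 3.
- *Level with 2/3 DLTs.* Level 1 0/3, level 2 2/3 (de-escalate), level 1 in total 0/6 or 1/6 (escalate): level 2 is named. The exact 95% interval for 2/3 is 9.4–99.2%, so this rests on three patients.
- *Order.* Final data are level 1 1/6, level 2 2/3. The order 0/3, 2/3, 1/3 (levels 1, 2, 1) names level 2. The order 1/3, 0/3, 2/3 (levels 1, 1, 2) names level 1.

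**Worked probabilities at assumed true rates 10/30/50%.** At 10%, P(0/3) = 0.729, P(1/3) = 0.243, P(2/3) = 0.027. At 30%, P(0/3) = 0.343, P(1/3) = 0.441, P(2/3) = 0.189.
- 0/3 then 1/6: 0.729 × 0.441 × 0.343 = 0.1103
- 1/6 then 0/3: 0.243 × 0.729 × 0.343 = 0.0608
- 2/9: 0.243 × 0.243 × 0.729 + 0.027 × 0.729 × 0.729 = 0.0574
- Sum, level not yet given: 22.8% (exact sum 0.2284)
- Level with 2/3 DLTs: 0.729 × 0.189 × (0.729 + 0.243) = 13.4%
- Order-dependent data set: 0.729 × 0.189 × 0.243 = 3.3% in each order

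**Range.** Exact enumeration of all three-cohort paths:

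| Assumed true DLT rates | Level not yet given | Level with 2/3 DLTs |
|---|---|---|
| 10/30/50% | 22.8% | 13.4% |
| 5/15/30% | 26.3% | 4.9% |
| 10/20/30% | 29.1% | 6.8% |
| 30/45/60% | 13.7% | 9.0% |
| 10/50/70% | 11.4% | 26.6% |
| 10/10/10% | 31.6% | 1.9% |
| 10/30% | 5.7% | 13.4% |
| 20/40% | 10.1% | 13.2% |
| 10/50% | 5.7% | 26.6% |
| 5/10% | 2.1% | 2.3% |

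The order-dependent data set has probability 0.3–6.6% in each order across these scenarios. With four levels at 10/20/30/40%, a level not yet given is named in 41.9%. With three levels at 10/20/30% but a start at level 2, it is 9.2%.

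**What the expansion adds.** A level not yet given when named gains 6–9 patients. A level at 2/3 then has 3 + 6 = 9 to 3 + 9 = 12. Section 9.3 reports the DLT rate and exact interval at each dose. If 9 expansion patients are treated at the 9.1.1 output, an isotonic estimate from all patients pooled (inverse-variance weights, closest to 30%) excludes the labelled level in 18.9% of trials at 10/30/50% (0.5–32.4% across the scenarios). The supplied text does not say what happens then.

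**The case against.** The strongest reply is that the label is an end-of-escalation label. A reader might infer that the trial could finish with an MTD that has no DLT data behind it. The documents do not support that: unless the expansion is stopped early, 6–9 patients are treated at the named level and their DLT rate is reported. This part of the reply stands. What remains is that no supplied passage lets those data revise the label. The related-event criterion of more than 40% in section 9.1 concerns long-term tolerability, and the monitoring committee's power to suspend accrual does not re-estimate an MTD.

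Second, only the statistical section of the SAP is supplied, and the IRB application refers to a clinical protocol. A revision rule could stand there, so the claim is limited to the supplied text.

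Third, a reader might infer that an isotonic estimate is simply more accurate than the table. It is not. At the same 9 patients, with a tie resolved to the 9.1.1 output if it is among the tied levels and otherwise to the lowest, it names the level truly closest to 30% less often than 9.1.1 at 10/30/50% (51.6 v 53.6%) and 5/15/30% (41.3 v 65.5%). It does so more often where toxicity is high (63.1 v 47.4% at 30/45/60%). Any gain from pooling at 10/30/50% comes from the extra patients.

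Fourth, the table's stopping at nine patients might look like a gap. It is not one: the table governs an escalation of up to nine evaluable patients, and nothing applies it to the pooled count.

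Finally, section 9.1 words the primary objective as toxicity and safety, which section 9.3 does report. That lowers the severity but does not remove the MTD from section 9.3 or from the Objectives.

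**Conclusion.** The concern holds in a limited form. Sections 9.1 and 9.3 define the estimated MTD as the last next-cohort output of Table 9.1.1, in conflict with the posterior wording in the IRB application. That output can be a level not yet given or one with 2/3 DLTs, and in one data set it turns on cohort order alone. These results follow from the plan's own table and need only two dose levels.

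The frequencies are illustrative: about 2–32% for a level not yet given (2–10% with two levels) and 2–27% for a level with 2/3 DLTs. They assume two or three levels, a start at the lowest, three full evaluable cohorts, and elimination that bars re-entry. The number of levels, starting level and DLT definition are not in the supplied text.

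The defect that survives the expansion is the missing route from expansion DLTs to the MTD and to the acute-safety declaration. This should be fixed; it does not undermine the escalation scheme itself.

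**What to change.** - Keep Table 9.1.1 for cohort assignment. Call its end-of-escalation output provisional, not the MTD estimate. The accuracy figures give no ground for replacing it at that point.
- Define the final MTD once, after the expansion, from all DLT-evaluable patients pooled across escalation and expansion, limited to levels with DLT data that are not eliminated. One example is the isotonic estimate closest to the stated 30% target.
- Write the weights and a tie rule in advance. At 10/30/50% the pooled estimate excludes the labelled level in 18.9% of trials with inverse-variance weights and 20.4% with patient-count weights.
- Base the final statement on acute safety of the top dose on the same pooled data.
- Reconcile the Objectives and Study Design sections of the IRB application and SAP sections 9.1, 9.2 and 9.3 to this one definition. How the expansion dose is chosen stays with the sponsor; no dose or clinical rule is proposed here.

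**Cost.** Wording and a short script, with no extra patients or visits. The final MTD statement waits for the expansion. After 9 pooled expansion patients, ties remain in 7.5% of trials at 10/30/50%, 11.5% at 5/15/30% and 30.0% at 5/10%. The final MTD may also be a level with fewer than the roughly 12 patients foreseen in section 9.2: at 10/30/50% the pooled estimate moves to a level with at most 6 evaluable patients in 17.4% of trials. What is gained is an MTD that always has DLT data behind it and, for given pooled counts, does not depend on cohort order apart from which levels were eliminated.

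### The expansion cohort is meant to confirm acute safety, but no prespecified DLT criterion lets its DLTs confirm or revise the MTD set at the end of escalation

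*Combined protocol and SAP*

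**What the plan says.** Section 9.1 sets a BOIN escalation with a 30% target DLT rate and cohorts of 3. It defines acute toxicity through the DLT rate among DLT-evaluable patients. The note under the section 9.1.1 table shows that the rules act after each escalation cohort. Section 9.1 then gives them a last use: "At the end of the dose escalation part of the study, we will use the dose escalation/de-escalation decision rules" to pick the expansion dose. The outcome is either that the highest dose is deemed safe for acute toxicity or that the recommended dose is the estimated MTD.

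Only after that does the expansion start. Its first listed purpose is that "an expansion cohort will be enrolled to confirm safety for acute toxicity", and section 9.2 repeats this. Section 9.2 plans up to 9 DLT-evaluable patients in escalation, 6 to 9 in expansion and 18 in total, with "about 12 patients treated at the MTD or the highest planned dose". The columns of the 9.1.1 table, headed "Number of patients Treated", run from 1 to 9.

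Four other provisions bear on expansion safety:
- Section 9.3 reports the DLT rate at each dose with an exact 95% confidence interval and refers MTD estimation back to 9.1.1.
- Section 9.1 declares the treatment not safe for long-term tolerability if more than 40% of patients at the expansion dose have related grade 3 or higher adverse events, or if more than 30% of patients have related grade 3 or higher CNS toxicity. The window is 90 days.
- Section 9.1 also has a halt: "Enrollment will be temporarily halted after the last patient of each cohort is enrolled until all current patients are DLT evaluable or withdrawn".
- The Data and Safety Monitoring section of the IRB application lets the DSMC, PRC, CCART or IRB suspend accrual at once for patient safety.

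**The concern.** To confirm something, a cohort needs a result that would count as confirmation and one that would not. The plan gives the expansion neither for DLTs. The verdict it is meant to test is already fixed, possibly on as few as 3 patients at the selected dose (3 + 9 = 12 is one way to reach the planned number). If the expansion produced many DLTs, section 9 would still carry forward the MTD or safe label given at the end of escalation. This touches the primary objective and the dose that the trial reports.

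**Working it through.** **Inputs.** From the documents: target φ = 0.30, cohorts of 3, expansion of 6 to 9, about 12 at the dose, and the printed table for n = 1 to 9. Assumed, because the documents do not state them: the usual BOIN defaults φ1 = 0.6φ = 0.18 and φ2 = 1.4φ = 0.42, and elimination when Pr(p > 0.30 | data) > 0.95 under a Beta(1,1) prior with n ≥ 3.

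**Step 1: reproduce the printed table.**
- λe = ln[(1−φ1)/(1−φ)] / ln[φ(1−φ1)/(φ1(1−φ))] = ln(0.82/0.70) / ln(0.246/0.126) = 0.2365
- λd = ln[(1−φ)/(1−φ2)] / ln[φ2(1−φ)/(φ(1−φ2))] = ln(0.70/0.58) / ln(0.294/0.174) = 0.3585

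Escalate if DLTs ≤ floor(0.2365n), and de-escalate if DLTs ≥ ceil(0.3585n). With the elimination rule, this gives:
- escalate: 0,0,0,0,1,1,1,1,2
- de-escalate: 1,1,2,2,2,3,3,3,4
- eliminate, from n = 3: 3,3,4,4,5,5,5

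Every printed cell matches.

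**Step 2: where the expansion falls.** Escalation may leave 3, 6 or 9 patients at the selected dose. Adding 6 or 9 gives 9 or 12, 12 or 15, and 15 or 18. Only 3 + 6 = 9 lies inside the table. The planned 12 is three columns past its end.

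**Step 3: carry the same formula to n = 10–18 (arithmetic only).**
- de-escalate at ≥ 4,4,5,5,6,6,6,7,7
- eliminate at ≥ 6,6,7,7,8,8,8,9,9

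At n = 12, 12 × 0.3585 = 4.30, so the de-escalate count is 5. The eliminate count is 7.

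**Step 4: how often the pooled 12 reach 5 DLTs when 9 expansion patients are added.** From 1/3 this is Pr(Bin(9,p) ≥ 4). From 0/3 it is Pr(Bin(9,p) ≥ 5).

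| True DLT rate | Entered with 1/3 | Entered with 0/3 |
|---|---|---|
| 30% | 0.27 | 0.10 |
| 40% | 0.52 | 0.27 |
| 50% | 0.75 | 0.50 |

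Entering with 2/6 or 1/6 and adding 9 gives the same two columns, because 6/15 then needs 4 or 5 of the 9.

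**Step 5: what the confidence interval can do.** The exact 95% interval for 5/12 is 15% to 72%. For 7/12, the eliminate count, it is 28% to 85%. Neither excludes 30%, so the interval alone cannot confirm or refute the verdict.

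**Step 6: what looks every 3 patients would cost, from 1/3 at a true rate of 30%.** In a cohort of 3, Pr(0), Pr(1), Pr(2), Pr(3) = 0.343, 0.441, 0.189, 0.027, so Pr(≥2) = 0.216.
- Eliminate row (≥4 at n = 6, ≥5 at n = 9): 0.027 + 0.441 × 0.027 + 0.189 × 0.216 = 0.080.
- De-escalate row (≥3 at n = 6, ≥4 at n = 9): 0.216 + 0.343 × 0.027 + 0.441 × 0.216 = 0.321.
- De-escalate row with n = 12 (≥5) added: trials not yet crossed at n = 9 hold 2 DLTs with probability 2 × 0.343 × 0.441 = 0.3025 and 3 DLTs with probability 0.343 × 0.189 + 0.441² = 0.2593. The further crossing is 0.3025 × 0.027 + 0.2593 × 0.216 = 0.064, for a total of 0.385.

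**The case against.** The best defence is that expansion patients are not unprotected.
- **Accrual.** A reader might infer that accrual cannot be paused. The documents do not support that: the oversight bodies may suspend accrual for safety, and the halt after each cohort is not expressly limited to escalation.
- **Use of the rules.** Nor are the 9.1.1 rules used only when escalation ends, since they also guide each escalation cohort.
- **Adverse-event criteria.** The 40% criterion is a numeric check on this very dose. At n = 12, more than 40% means at least 5 patients, the same count as the de-escalate boundary.
- **Table and reporting.** The table does cover 3 + 6 = 9 patients, and section 9.3 does not confine the DLT rate to escalation patients.
- **Missing text.** Only section 9 and the IRB application are available. The DLT definition and the dose-level sections are not.

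All of this stands as far as it goes, and it rules out saying that there is no check at all. It does not close the gap. The suspension power has no DLT criterion. The halt waits for evaluability, and no expansion decision follows it. The adverse-event criteria count events other than DLTs, give a long-term verdict and state no interim look. The IRB application's Study Design section bases the MTD on the posterior DLT probability, but it too establishes the MTD before expansion begins.

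**Conclusion.** The point holds in this form: in the supplied text, no prespecified DLT-based criterion lets the expansion confirm or revise the MTD or acute-safety verdict fixed at the end of escalation. The main gap is the missing instruction to use expansion DLTs. The table ending at 9 is secondary, because its formula extends directly.

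The size depends on the entry data and the true rate. With 9 added, the chance that the pooled data reach the design's own de-escalate count runs from 0.10 (0/3, true rate 30%) to 0.75 (1/3, true rate 50%), with no stated consequence for the MTD. These figures rest on the assumed BOIN defaults, on independent patients with a common DLT rate, and on all 9 expansion patients being DLT-evaluable. How often the dose would be selected on only 3 patients cannot be computed, because the number of dose levels is not given.

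A reader might go further and infer that the de-escalate row should simply be enforced every 3 patients at little cost. The numbers do not support that: from 1/3, it would be crossed at n = 6 or 9 in 32% of trials at a dose exactly on target.

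**What to change.** Reconcile the end-of-escalation MTD rule in 9.1 and 9.3 with the expansion's stated purpose. Base the final MTD or acute-safety statement on the pooled DLT-evaluable escalation and expansion patients at that dose, with the 9.1.1 table carried by its own formula to the planned number. Say which pooled result counts as confirming acute safety. State the BOIN parameters so that the extension is not left to assumption. Use one evaluability definition: 9.1 refers to the first 30 days, whereas the IRB application's expansion wording refers to planned dosing without that window.

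Separately, state whether the 9.1.1 rules and the cohort halt apply during expansion. Any accrual rule is the sponsor's choice and should be made with both costs in view: from 1/3 at a true 30% rate, the eliminate row at n = 6 and 9 is crossed in 8% of trials, and the de-escalate row in 32% (0.385 by n = 12).

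The cost is SAP wording and up to nine more table columns. The final statement may also be less favourable than the one made at the end of escalation. For a dose truly at 30% entered with 1/3, the pooled 12 would reach the de-escalate count in 27% of trials.

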## Day 30-60-90 Expidiolex administrations

- · Administration of epidiolex
- · Evaluation of any symptoms known as adverse events
- Evaluating dose level based on symptoms
- · Making sure you are following instructions
- · One blood draw for PSA test and total testosterone as a standard part of treatment
- · All the above scans can be repeated per NCCN guidelines or more often as clinically indicated by suspected disease progression.
- o PET or PET/CT scan at the PI's discretion
- o Bone scan at the PI's discretion
- o CT chest, abdomen, pelvis scans at the PI's discretion
- o MRI of the pelvis
- Assessment of the disease progression
- EKG a test that measures the heartbeat.
- · CBC: A routine blood test used to measure the ratios of different blood cell counts to see if any are out of alignment
- · CMP: A routine blood test used to examine overall metabolism and identify any potential problems
- · Venipuncture for the blood tests described above
- Concomitant Medications where the doctor will assess any current medications to make sure nothing will have side effects with the Epidiolex.
- Physical exams with vitals determined and ECOG performance evaluation

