## 30 days after treatment

- Evaluation of any symptoms known as adverse events
- One blood draw for PSA test and total testosterone as a standard part of treatment

- All the above scans can be repeated per NCCN guidelines or more often as clinically indicated by suspected disease progression.
- o PET or PET/CT scan at the PI's discretion
- o Bone scan at the PI's discretion
- o CT chest, abdomen, pelvis scans at the PI's discretion
- o MRI of the pelvis
- CBC: A routine blood test used to measure the ratios of different blood cell counts to see if any are out of alignment as determined by the PI
- CMP: A routine blood test used to examine overall metabolism and identify any potential problems as determined by the PI
- Physical exams with vitals determined and ECOG performance evaluation as determined by the PI.

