During the study, information will be collected to assess compliance with the study requirements. These records will be used by the FDA, the IRB, and the Investigator(s) in connection with complying with their obligations relating to this study. The records will not be used for any other purposes or disclosed to any other party without the subject's permission. All records will be coded with an identification number to protect their identity. Data will be stored in a secured area for at least two years after the study is completed. All data stored is on site at Markey Cancer Center Clinical Research Organization in locked facilities, and with limited access to records by designated research staff. All research records will be held for a minimum of six years following completion of the study Patients enrolled in this study will be evaluated clinically and with standard laboratory tests before and at regular intervals during their participation in this study. Safety assessments will consist of monitoring and recording of all Adverse Events (AEs) and all serious adverse events (SAEs); measurement of protocol-specified hematology, clinical chemistry, and urinalysis variables; measurement of protocol-specified vital signs; and other protocol-specified tests that are deemed critical to the safety evaluation of the study drug(s). Patients will be evaluated for all adverse events for the duration of their participation in the study. Patients discontinued from the treatment phase of the study for any reason will be evaluated approximately 30 days (between 30 and 37 days) after the decision to discontinue treatment.

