# 9.4 Analysis of Secondary Endpoints

Change in serial PSA, PSA velocity and testosterone levels from baseline throughout the 90-day treatment period will be represented by longitudinal profiles and analyzed by mixed effects model. Baseline is defined as the last non-missing PSA measurement prior to administrating Epidiolex. PSA and testosterone levels may be categorized and summarized by response rates with confidence intervals. Patients who are DLT evaluable, have baseline measurement and have at least one post-baseline measurement will be included in the analysis of secondary endpoints.

The health-related quality of Life (EORTC QLQ-C30 and QLQ-PR25) collected longitudinally will be analyzed using appropriate linear models for repeated measures data.

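### Section 9.1's 90-day safety window most naturally ends with treatment, so a completer's related grade 3+ events starting after day 90 are collected but not counted

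*Combined protocol and SAP*

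**What the plan says.** Section 9.1 evaluates long-term safety and tolerability through "summary statistics of adverse events occurred within the 90-day follow-up period in patients who received any amount of study drug". Two criteria follow, and meeting either one makes the treatment not safe for long-term tolerability. The first is met if more than 40% of patients at the expansion dose have a treatment-related event of grade 3 or higher. The second is met if more than 30% of patients have treatment-related CNS toxicity of grade 3 or higher. Neither criterion restates a window, and 9.1 does not say on which day the 90 days begin.

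Section 9.4 analyses PSA and testosterone "throughout the 90-day treatment period". The Research Procedures list on-treatment visits under "Day 30-60-90 Expidiolex administrations" and one later visit under "30 days after treatment", whose first item is "Evaluation of any symptoms known as adverse events". The safety text under Records, Privacy, and Confidentiality (Digital Data) adds "Patients will be evaluated for all adverse events for the duration of their participation in the study". It also says that patients discontinued from the treatment phase "will be evaluated approximately 30 days (between 30 and 37 days) after the decision to discontinue treatment".

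**The concern.** The safety window and the treatment period are both 90 days, yet adverse events are collected for about 30 days longer. If the window starts at first dose, it closes as a completer finishes treatment. A related severe event that starts in the following month is then recorded but stays outside the rule.

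Long-term safety and tolerability is part of the primary objective stated in 9.1, and these two criteria are the only rule that gives a verdict on it. Leaving events out can only lower the count. Coverage after treatment also differs between patients: early stoppers have it inside the window and completers do not.

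**Working it through.** **1. The plan's sample size.** Sections 9.1 and 9.2 give up to 9 evaluable patients in escalation, in cohorts of 3, and 6 to 9 in expansion. 9 + 9 = 18 enrolled, as stated. 3 (one escalation cohort at the selected dose, an assumption) + 9 = 12, which matches the stated figure of about 12 at the MTD or highest dose. The plan gives no operating characteristics for the two criteria, so there is nothing further to reproduce.

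**2. Day count, with the window starting at first dose.**
- The window ends at day 90.
- A completer's post-treatment visit falls at 90 + 30 = day 120. If the 37-day upper limit for discontinued patients were applied, it would be 90 + 37 = day 127.
- For a patient who stops early, the visit lies inside the window if he stops by day 90 − 30 = 60 (visit at 30 days) or day 90 − 37 = 53 (visit at 37 days).

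The uncounted interval for a completer is therefore day 91 to about day 120. For a patient who stops by about day 53 to 60 there is none.

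**3. Events needed to meet each criterion.**

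| Criterion | Denominator | Not met | Met |
|---|---|---|---|
| >40%, related grade 3+ | 12 | 4/12 = 33.3% | 5/12 = 41.7% |
| >30%, related grade 3+ CNS | 12 | 3/12 = 25.0% | 4/12 = 33.3% |
| >30%, related grade 3+ CNS | 18 | 5/18 = 27.8% | 6/18 = 33.3% |

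The CNS criterion does not say which patients form its denominator, so both are shown. In every row, one patient decides the result.

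**4. Size for the 40% criterion.** The documents give neither a 90-day event rate nor a late-event rate, so both are assumed. Let r be the proportion with a related grade 3+ event by day 90, and f the ratio of the post-treatment to the on-treatment hazard (constant hazards). Counting 30 more days multiplies the cumulative hazard by 1 + f × 30/90, so

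q = 1 − (1 − r)^(1 + f/3), and the chance of meeting the criterion is P(Bin(12, q) ≥ 5).

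For example, with r = 0.30 and f = 0.5, q = 1 − 0.70^(1.1667) = 0.340 and the chance is 0.39.

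| r by day 90 | f = 0 (also the 90-day rule) | f = 0.25 | f = 0.5 | f = 1 |
|---|---|---|---|---|
| 0.30: q | 0.300 | 0.320 | 0.340 | 0.378 |
| 0.30: chance | 0.28 | 0.33 | 0.39 | 0.50 |
| 0.35: q | 0.350 | 0.373 | 0.395 | 0.437 |
| 0.35: chance | 0.42 | 0.48 | 0.55 | 0.66 |
| 0.45: q | 0.450 | 0.477 | 0.502 | 0.549 |
| 0.45: chance | 0.70 | 0.76 | 0.81 | 0.89 |

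The model treats every patient as a completer, so it gives the largest change for each f.

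**5. A second model of late events.** Suppose instead that 5%, 10% or 15% of patients who are event-free at day 90 have a first event afterwards. At r = 0.30 the rate becomes 0.30 + 0.70 × (0.05, 0.10, 0.15) = 0.335, 0.370, 0.405. The chance of 5 or more of 12 rises from 0.28 to 0.37, 0.48 and 0.58, which is the same direction.

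**The case against.** **The start of the window is inferred.** Section 9.1 calls it a follow-up period and gives no start day. Only section 9 of the clinical protocol is available here, and a definition may stand elsewhere. This objection stands as a qualification. First dose remains the natural reading, because a 90-day window after treatment would have no scheduled visit in its last two months. On either reading the text should state the start and end.

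**Onset, not detection.** A reader might infer that everything found at the post-treatment visit is dropped. The text does not support this, because 9.1 counts events that occurred within the period. An event that starts by day 90 and is recorded later still counts.

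**Late events are not lost.** They are collected, and 9.3 summarises adverse events for long-term safety without repeating the 90-day limit. That is correct, but a descriptive summary does not put them into the 40% and 30% criteria.

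**A longer window with the same limits is a stricter rule.** A fixed 90-day risk is a legitimate quantity. At r = 0.30 every extended rate in the first model stays below 40%, yet the chance of a not-safe verdict rises to as much as 0.50. At r = 0.35 only the equal-hazard case crosses 40%. This stands and is the real cost of the change. Against it, the criteria already require relatedness, so only related events that actually occurred are added. Where the 90-day rate is already over the limit (r = 0.45), the chance of detecting it rises from 0.70 to between 0.76 and 0.89 when there are late events.

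**Conclusion.** The point holds for patients who complete treatment, on the reading that the 90 days run from first dose. For them, related grade 3+ events with onset from day 91 to about day 120 are collected but left out of both criteria. Patients who stop by about day 53 to 60 already have that period counted.

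The direction is certain, since the omission can only lower the count, and a single event can change the verdict at the planned numbers. The size is not known. Across the assumed hazard ratios above zero, the chance of meeting the 40% criterion differs by about 0.06 to 0.22 at a 30% 90-day rate and by about 0.07 to 0.25 at 35%. It does not differ at all if no events start after treatment.

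A reader might go further and conclude that the rule has been shown to pass an unsafe treatment. The documents do not support that: they give no late-event rate, and several of the scenarios stay under the plan's own limit even when late events are counted. This is a cheap improvement, not a flaw that invalidates the safety evaluation.

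**What to change.** In 9.1, define the window for both criteria as first dose through the post-treatment safety visit. That is about 30 days after treatment ends for completers, and 30 to 37 days after the decision to discontinue for patients who stop early. State that events are assigned by date of onset. Report the 90-day proportion alongside as a supporting summary. Reconcile the term follow-up in 9.1 with the treatment period in 9.4 and with the visit schedule.

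The change is to SAP wording only: the visit and its adverse-event assessment are already planned, so no patients, visits or data are added. The price is a somewhat stricter rule at unchanged limits. At a 30% 90-day rate the chance of a not-safe verdict on the 40% criterion goes from 0.28 to 0.33, 0.39 or 0.50 at a quarter, half or equal late hazard. The sponsor should adopt the wider window knowing this, and before the criteria are applied to the data.
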